# 1 Protocol Overview

Study Description	The purpose of this study is to identify a tolerable dose for postpartum ketamine infusion using a maximum tolerated dose (MTD) 3+3 design. A loading dose over 1 hour will be the MTD variable to be tested, as our data suggest that ketamine side effects occur with the loading dose.
Study Population:	Patients having cesarean delivery (CD) who are either: 1) planning not to breastfeed; or 2) are receiving ketamine as part of clinical care, will be enrolled. Ketamine will be started in postpartum patients, after cord clamping.
Planned Sample Size:	The projected sample size will be a maximum of 12 patients with complete primary outcome data within the MTD 3+3 design.
Participating Institutions (if a multicenter clinical trial)	N/A

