#### 2.2 Rationale

Defining postpartum ketamine tolerable doses and ketamine PK is critical to understanding the potential role of ketamine for PPD prevention, and to understanding the plasma ketamine concentration time profile with its maximum tolerated dose. There are no PK/PD models for ketamine-induced side effects or analgesia, although there are isolated reports of ketamine side effects with plasma concentrations. Available trials that conclude ketamine is "well tolerated" did not query patient perspectives in side effect acceptability. The duration of ketamine exposure may be important as well, given that subcutaneous administration may have greater antidepressant duration than intravenous administration of the same dose, despite lower peak plasma concentrations in subcutaneous administration. These knowledge gaps are significant because they limit patient-centered acceptability of ketamine and a finer understanding of its potential effective utility for PPD prevention. Because ketamine is metabolized by CYP3A and CYP2B6 (increased activity in pregnancy and immediately after delivery), and because pregnancy induces sensitivity to anesthetics, it is critical in this project to identify a tolerable dose of postpartum ketamine and the perioperative factors impacting its PK.

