# Protocol Overview.

Patients will respond to surveys prior to and following cesarean delivery regarding their current pain and mood. Patients will begin study procedures in the third trimester of pregnancy, within approximately one week of scheduled cesarean delivery, until 12-weeks postpartum.

Preoperative weight and vital signs will be measured, and baseline inventories completed (Figure 1; refer to section 1.1). After delivery, cord clamping and declaration of clinical stability by the anesthesiologist (typically~5-15 min after delivery; ±30 minutes), a loading infusion of ketamine 0.05 mg/kg/hour will begin for the first 3-patients in the study. Vital signs and side effect symptomology will be measured 15, 30, and 60 minutes (±5 minutes) after infusion start, and at 4, 8, 10, 12, 16, and 24 hours (±30 minutes) after infusion start. Plasma samples will be collected at 1, 6, 10, and 12 hours (±30 minutes) after infusion. Any report of adverse events or side effects will trigger a blood draw for analysis and correlation of these symptoms to plasma levels of ketamine within the 12-hour infusion. All assessments have been timed to coincide with timing intervals of typical post-CD clinical care interventions. Patients dosing after the first three patients will proceed based on the MTD protocol in Figure 2; refer to section 1.1.

MTD dosing protocol.

A loading dose and maintenance infusion strategy will be used (Figure 2; in section 1.1). MTD to be tested will focus on the initial loading dose used to achieve a higher plasma concentration in a brief period. Ketamine dose will not exceed sub-anesthetic ranges (≤0.2mg/kg/hr). The maintenance rate of 0.05mg/kg/hr is based on our preliminary data suggesting tolerability, and on data suggesting that this rate might yield adequate plasma concentrations necessary for the treatment of depression. The first set of 3 patients will receive a loading infusion of ketamine 0.05 mg/kg/hr for the first data. The decision to escalate the loading infusion dose, enter 3 more at the same level, or stop, will not occur until 3 patients complete the 0.05 mg/kg/hr protocol. A **DLT** event is defined in section 3.4.1.

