# 6.2 Study Drug Preparation and Dispensing

The study drug, ketamine, will be sourced by investigational (IDS) Pharmacy at UPMC Magee Women's Hospital. The infusions will be packaged and labeled for use in the clinical research study per pharmacy protocols and guidelines. Ketamine will be prepared by pharmacy with dosing instructions. There will be no blinding.

For on-site preparation and dispensing of the study drugs, the following procedures will be followed. The pharmacist of record will: maintain adequate records confirming receipt, expiration dates, or other disposition information on the investigational drug; they will record the name of the individual to whom the drug is shipped, date, quantity, and batch number. They will secure the drug in a locked storage area and monitor to ensure proper storage conditions; they will also complete regular inventory to assure accurate indication of stock on hand, as well as proper recording of stock received, dispensed, and returned. For the patients enrolled for open label pharmacokinetic studies, the pharmacist will generate a label prior to dispensing the study drug, including the date dispensed, quantity and expiration information, drug strength and dose; they will affix the label to the dispensed drug. For dispensing and drug disposition recording, they will record the date dispensed, patient initials or other identifiers, drug treatments, quantity dispensed, initials of dispenser, date and amount of patient returns documented in study records (i.e., returned drug that cannot be re-dispensed). Filing and all drug documentation will occur within study records, medical records, and logs.

Following the cesarean delivery, the initial drug administration (via IV infusion) will begin 15 minutes (± 30 minutes) after cord clamping and declaration of clinical/ hemodynamic stability by the case anesthesiologist after delivery. The maintenance dose will start 60 min (range: +15min) after the initial loading dose. The infusion will be completely stopped 12 hours after the start of infusion. The same infusion pump will follow the patient throughout the postoperative period for 12 hours until completion of the study drug. No manipulation of the infusion pump will occur by the patient. Adjustments to the rate will be at the discretion of the study team and can be physically made by study personnel qualified and trained in these procedures, or by clinical care providers under direct orders from the study team.

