# Ketamine Infusion, Side Effect Measures, and Plasma Sampling Procedures.

Preoperative weight and vital signs will be measured, and baseline inventories completed (Figure 1). After delivery, cord clamping and declaration of clinical stability by the anesthesiologist (approximately 5-15 minutes after delivery, ± 30 minutes), a loading infusion of ketamine 0.05 mg/kg/hr will begin for the first 3-patients in the study. Vital signs and Richmond Agitation Scale (RASS), and self-reports of side effects will be measured 15, 30, and 60 minutes (±10 minutes) after infusion start, and at 4-8-10-12-16-24- hours (±30 minutes) after infusion start. Plasma samples will be collected at 1-6-, 10- and 12- hours (±30 minutes) after infusion start via an indwelling IV catheter to facilitate ease of access. Plasma samples at 1-6-, 10- and 12- hours after infusion start will be used to calculate Cmax, AUC, and Css and to correlate DLTs with these PK parameters. Any report of adverse events or side effects will trigger a blood draw for analysis and correlation of these symptoms to plasma levels of ketamine. All assessments have been timed to coincide with timing intervals of typical post-CD clinical care interventions. Patient dosing after the first three patients will proceed based on the MTD protocol in Section 1.1.

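### The ±30-minute window on the 1-hour plasma draw lets the only scheduled sample of load exposure fall 45 minutes before to 30 minutes after the load ends, and the 12-hour sample can follow pump stop

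*Combined protocol and SAP*

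**What the plan says.** Section 1 names the tested variable: "A loading dose over 1 hour will be the MTD variable to be tested". Section 6.2 sets when it ends: "The maintenance dose will start 60 min (range: +15min) after the initial loading dose". The pump stops at 12 hours (Sections 6.2 and 7.3).

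Section 7, under Ketamine Infusion, Side Effect Measures, and Plasma Sampling Procedures, sets the draws: "Plasma samples will be collected at 1-6-, 10- and 12- hours (±30 minutes) after infusion start via an indwelling IV catheter". The same paragraph gives their use: "Plasma samples at 1-6-, 10- and 12- hours after infusion start will be used to calculate Cmax, AUC, and Css", and goes on to plan a correlation of DLTs with those parameters.

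The vital-sign and side-effect check at 60 minutes has a tighter window: ±5 minutes in Section 4 and ±10 minutes in Section 7. An unscheduled sample is also taken whenever a side effect or adverse event is reported (Sections 4 and 7, Appendix 2 footnote b).

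I found no statement that actual draw, rate-change or stop times are recorded or used in the PK calculations. Section 12 has no PK method. PK is not among the objectives or endpoints in Section 3, although Section 2.2 says: "Defining postpartum ketamine tolerable doses and ketamine PK is critical".

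**The concern.** Section 4 gives the purpose of the load as reaching a higher concentration quickly. Between infusion start and 6 hours there is one scheduled sample, so that sample alone describes what the load did. Its window is as wide as half the load. One patient could be sampled when less than half the load is in, and another when already on maintenance, and both values would be filed as the 1-hour level. The 12-hour sample has a similar problem: it feeds Css, yet it may be taken while the drug is washing out.

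At stake is how well the trial can describe load exposure and relate it to DLTs. With at most 12 patients, little averaging is available to absorb timing differences.

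**Working it through.** The documents give no half-life, Cmax or PK precision, so there is no planned figure to reproduce.

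**Inputs from the documents.** Draws at 1, 6, 10 and 12 h, each ±30 min (Section 7). Load ends at 60 to 75 min (Section 6.2). Maintenance rate and first loading rate both 0.05 mg/kg/hr, with a ceiling of 0.2 mg/kg/hr (Section 4). Pump stop at 12 h.

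**Assumptions, not in the documents.** One compartment; half-life 1.5 to 3 h; loading rates above 0.05 taken as 0.10, 0.15 and 0.20 mg/kg/hr, because Figure 2 is not shown.

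**Step 1: the window.** The 1-hour draw falls at 60 − 30 = 30 min to 60 + 30 = 90 min. Relative to the end of the load, the earliest is 30 − 75 = −45 min and the latest is 90 − 60 = +30 min. The 12-hour draw falls at 11.5 to 12.5 h. This step needs no kinetic assumption.

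**Step 2: the 1-hour value.** With loading rate R, maintenance rate M, load duration T and k = ln 2 / half-life:

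- during the load, C(t) = (R/CL)(1 − e^(−kt));
- after it, C(t) = C(T)e^(−k(t−T)) + (M/CL)(1 − e^(−k(t−T))).

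Clearance CL cancels in every ratio.

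- Lowest: 30-min draw, 75-min load, half-life 3 h: (1 − 2^(−0.5/3)) / (1 − 2^(−1.25/3)) = 0.1091 / 0.2509 = 0.43. At half-life 1.5 h it is 0.2063 / 0.4388 = 0.47. With a 60-min load the corresponding values are 0.53 and 0.56.
- Highest: 90-min draw, 60-min load, rate 0.05 (equal to maintenance, so the level simply keeps rising), half-life 3 h: 0.2929 / 0.2063 = 1.42.
- 90-min draw at rate 0.20, 60-min load, half-life 1.5 h: end of load 0.20 × 0.3700 = 0.0740; 30 min later 0.0740 × 0.7937 + 0.05 × 0.2063 = 0.0690; ratio 0.93.

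The overall range is 0.43 to 1.42. The top end belongs to the first dose level. At 0.10, 0.15 and 0.20 the upper limits are 1.16, 1.07 and 1.02, so the main risk at escalated loads is an early draw that reads low.

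**Step 3: Cmax as the largest of the four samples.** Only the 1-hour draw time is varied. Example: load 0.20 for 75 min, half-life 1.5 h. The true peak is 0.20 × 0.4388 = 0.0878. A 30-min draw gives 0.20 × 0.2063 = 0.0413. The 6-h level is 0.0878 × 0.1114 + 0.05 × 0.8886 = 0.0542, the largest of the four. Observed over true = 0.0542 / 0.0878 = 0.62. For load 0.15 it is 0.0518 / 0.0658 = 0.79. For load 0.10 the 12-h level (0.0500) exceeds the end-of-load level (0.0439), so nothing is lost.

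Worst observed/true Cmax, 60-min load / 75-min load:

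| Load (mg/kg/hr) | 1.5 h | 2 h | 2.5 h | 3 h |
|---|---|---|---|---|
| 0.05 | 1.00 / 1.00 | 1.00 / 1.00 | 1.00 / 1.00 | 1.00 / 1.00 |
| 0.10 | 1.00 / 1.00 | 1.00 / 1.00 | 1.00 / 1.00 | 1.00 / 1.00 |
| 0.15 | 0.91 / 0.79 | 1.00 / 0.96 | 1.00 / 1.00 | 1.00 / 1.00 |
| 0.20 | 0.71 / 0.62 | 0.88 / 0.77 | 1.00 / 0.89 | 1.00 / 1.00 |

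Sensitivity: with a 60-min load, the end-of-load level exceeds the 12-h level only if half-life is below about 1.0 h (load 0.10), 1.7 h (0.15) or 2.4 h (0.20). Below the assumed range, at 0.25 to 1 h, observed Cmax at 0.20 can drop to 0.45 of true.

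**Step 4: the 12-hour sample.** After pump stop C falls as 0.5^(time/half-life). At 12.5 h: 0.5^(0.5/1.5) = 0.79 and 0.5^(0.5/3) = 0.89 of the 12-h level.

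**The case against.** The strongest reply is that Cmax comes from four samples, not one. A reader might infer from the roughly twofold swing in the 1-hour value that measured Cmax can double or halve with draw time. Within half-lives of 1.5 to 3 hours it cannot. At loads of 0.05 and 0.10 the late samples set Cmax and the 1-hour timing does not matter, and the worst cell in the table is 0.62. That part of the reply stands. It leaves the 1-hour value itself exposed: where late samples set Cmax, that Cmax mainly describes maintenance, and the 1-hour value remains the only scheduled measure of the load.

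A reader might also infer that the DLT correlation would be mostly timing error. The documents do not support that. They give no between-patient variability, no distribution of draw times and no expected DLT rate, and the ratios above are window extremes rather than typical errors.

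Event-triggered draws give a concentration at the time of symptoms that does not depend on the 1-hour window. This is a real mitigation, but only patients with events have such samples. A correlation also needs comparable values from patients without events, and only the scheduled draws supply those.

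Finally, Section 7 says assessments were timed to fit routine post-cesarean care, which is a fair reason for a generous window. The tighter window already set for the 60-minute check suggests that something closer is workable.

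**Conclusion.** The point holds in a limited form. The window arithmetic is certain: the sole scheduled sample of load exposure can miss the end of the load by 45 minutes on one side and 30 on the other, and the 12-hour sample can follow pump stop by 30 minutes.

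The size rests on assumed kinetics and assumed dose levels above the first. With one compartment and half-life 1.5 to 3 hours, the 1-hour value lies between 0.43 and 1.42 of the end-of-load level, and a late 12-hour draw reads 79 to 89% of the level at pump stop. Cmax is understated only at the higher assumed loads with faster kinetics: to 0.79 of true at 0.15 and 0.62 at 0.20, both at half-life 1.5 hours with a 75-minute load. The planned correlation of DLTs with load exposure may therefore be distorted by timing; how much cannot be derived from the documents.

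It would be wrong to infer that the MTD is at risk. Escalation depends on DLT counts, PK is not a listed endpoint, and with at most 12 patients and no power calculation the correlation is descriptive in any case. This is a worthwhile, inexpensive improvement, because draw times that were not recorded may not be recoverable later.

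**What to change.** In the Section 7 sampling paragraph, with matching text in Section 4 and Appendix 2:

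- Take the first sample within about 5 minutes before the actual change from load to maintenance rate, and call the result 'end-of-load concentration'. Under the same assumptions, a draw 5 minutes early reads 0.93 to 0.95 of the end-of-load level.
- Take the 12-hour sample before the pump stops.
- Record the actual times of each draw, of every rate change and of pump stop, and use them in the AUC and Css calculations.

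The cost is a tighter window on two draws that are already planned, and somewhat more late samples to log. No draw is added and no dose or clinical rule changes.

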# 3 Hypotheses, Objectives and Endpoints

# 3.1 Hypotheses

# 3.2 Primary Hypothesis

The purpose of this study is to identify a tolerable dose for postpartum ketamine infusion using a maximum tolerated dose (MTD) 3+3 design. A loading dose over 1 hour will be the MTD variable to be tested, as our data suggest that ketamine side effects occur with the loading dose.

Our working hypothesis, based on our preliminary PK and safety data and that of Loo et al [19], is that a 12-hr IV ketamine infusion of 0.05 mg/kg/hour is the MTD.

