# 3.4 Endpoints

# 3.4.1 Primary Endpoint

Maximum Tolerated Dose (MTD). The MTD will be defined as the dose at which fewer than 33% of patients experience a DLT defined by intolerability.

Tolerability (dichotomous Yes/No)

Tolerability (YES) will be defined as: lack of adverse events (adverse event defined as: severe unresolved hemodynamic effect: systolic blood pressure <80 or >160, heart rate <40 or >120).

Lack of Tolerability will be defined as presence of any adverse event (i.e., severe unresolved hemodynamic effect: systolic blood pressure <80 or >160, heart rate <40 or >120).

A **DLT** event is defined by complete infusion cessation due to intolerable side effect acceptability ratings by patient, OR the experience of an intolerable event as defined above. The escalation of dosing will be as noted in Figure 2 and is based on a modified Fibonacci sequence  $^{101,102}$  with smaller proportional increases in dose in the escalation scheme. Escalations occur until 2 in a cohort of 3 to 6 experiences DLT (i.e., until  $\geq$ 33% of patients experience DLT at that dose). The dose **below** this level estimates the MTD.

Participants will be classified as having had a DLT if any of the following conditions are met:

- Persisting (i.e., unresolved after 3 consecutive measurements within a 15-minute interval)
  hemodynamic side effects defined as below and despite treatments or minimizing
  infusion rates as specified.
  - Systolic blood pressure <80 or >160
  - Heart rate <40 or >120
- Complete infusion cessation due to intolerable side effect acceptability ratings by patient

Primary Outcomes will be measured at a minimum of every 4-hours from the start of the ketamine infusion (t = 0) for 24-hours (12-hours post infusion cessation). Additional assessments will be administered between the 4-hour measurements if any adverse event or side effect is noted by the patient.

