If RASS -2 or below, OR Respiratory Rate is < 8	Hold infusion for 10 minutes - symptom recheck every 10 min until resolution	If no resolution within 1 hour:  D/C infusion based on investigator discretion and monitor subject for safety as described in Section 7.4 and 7.5	↓ dose by 50% (e.g., 0.05mg/kg/hr reduced to 0.025 mg/kg/hr) and continue infusion.	If no resolution within 1 hour:  D/C infusion based on investigator discretion and monitor subject for safety as described in Section 7.4 and 7.5	↓ dose by 50% (e.g., 0.025mg/kg/hr reduced to 0.013 mg/kg/hr) and continue infusion.	D/C infusion and monitor subject for safety as described in Section 7.4 and 7.5 Event qualifies as DLT
Dizziness, lightheadedness, bad dreams, persistent itchiness, hallucinations, nausea, vomiting, or other side effects rated by patient as Not Acceptable	Hold infusion for 10 minutes - symptom recheck every 10 min until resolution Supportive care medications in 9.1	If no resolution within 1 hour:  D/C infusion based on investigator discretion and monitor subject for safety as described in Section 7.4 and 7.5	↓ dose by 50% (e.g., 0.05mg/kg/hr reduced to 0.025 mg/kg/hr) and continue infusion.	If no resolution within 1 hour:  D/C infusion based on investigator discretion and monitor subject for safety as described in Section 7.4 and 7.5	↓ dose by 50%     (e.g.,     0.025mg/kg/hr     reduced to 0.013     mg/kg/hr) and     continue     infusion.	D/C infusion and monitor subject for safety as described in Section 7.4 and 7.5 Event qualifies as DLT
Nausea or Vomiting	Rescue medications as indicated in 6.6  Re-evaluate for symptom resolution 10 min after rescue medication  Hold infusion for 10 minutes - symptom recheck every 10 min until resolution	If no resolution within 1 hour:  D/C infusion based on investigator discretion and monitor subject for safety as described in Section 7.4 and 7.5	dose by 50%  (e.g., 0.05mg/kg/hr  reduced to 0.025  mg/kg/hr) and  continue  infusion.	If no resolution within 1 hour:  D/C infusion based on investigator discretion and monitor subject for safety as described in Section 7.4 and 7.5	dose by 50%  (e.g., 0.025mg/kg/hr  reduced to 0.013  mg/kg/hr) and  continue  infusion.	D/C infusion and monitor subject for safety as described in Section 7.4 and 7.5 Event qualifies as DLT

Figure 3. Dose adjustments based on patient-reported acceptability

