# 7 Research Activities

Figure 1 (section 1.1) illustrates all encounters for measurements at the preoperative baseline, during the intraoperative period, ketamine infusion period, in the postpartum hospital stay (or until patient discharge), and the 1- to 12-week assessments of pain and depression. Study procedures will begin at enrollment pre-operatively, continue during the ketamine infusion, and hospital post-operative stay, continue weekly in the postpartum period, and end at 12-weeks postpartum.

Information collected at baseline includes maternal demographic information, prenatal pain and depressive symptomology, concurrent acute pain, and covariables such as demographic characteristics, and perceived stress. EPDS is completed twice, at least 1 week apart, prior to delivery. The baseline measures are repeated weekly in the postpartum period until 12-weeks postpartum.

During the ketamine infusion, blood samples will be taken at 1-, 6-, 10-, & 12-hours post-infusion start, as well as at the time of any adverse side effect report to assess ketamine/metabolite levels at the time of event.

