### 7.4 Safety Assessments/Procedures During Treatment

Maternal monitoring during the infusion will follow our clinical standards perioperative ketamine monitoring and the standard Magee system safety precautions for administration of a controlled substance will be in place to protect from any misuse. A licensed and qualified anesthesia provider (resident, fellow, nurse anesthetists, or anesthesiologist) will be present during the first 30 minutes of the infusion and will have the option to treat blood pressures >180/100 mm Hg or heart rate >110 bpm. The study infusion will be discontinued if 3 consecutive measurements within a 15-minute interval remain above protocol-defined limits despite intervention (section 6.3). Maternal side effect symptomology monitoring will occur throughout the ketamine infusion. Automated alerts for maternal side effect responses go to clinical and research staff for immediate action. Any report of side effects will trigger a blood draw for analysis and correlation to measured plasma levels.

An independent DSMB will define frequency of monitoring of tolerability and DLT data. The severity of adverse events are classified in section 10.1

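### The planned correlation of DLTs with AUC and Css uses exposure that a DLT during the infusion has itself cut short

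*Combined protocol and SAP*

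**What the plan says.** In Section 7, under the heading on ketamine infusion, side effect measures and plasma sampling, the scheduled samples "will be used to calculate Cmax, AUC, and Css and to correlate DLTs with these PK parameters". The introduction to Section 7 gives the times: "blood samples will be taken at 1-, 6-, 10-, & 12-hours post-infusion start".

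Four other places determine what happens to exposure in a patient with a DLT.

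- Section 3.4.1 defines one limb of the DLT as "complete infusion cessation due to intolerable side effect acceptability ratings by patient". The other limb is a persisting blood pressure or heart rate abnormality. Observation runs for 24 hours, twice the length of the infusion.
- Section 7.4, for hemodynamic events: "The study infusion will be discontinued if 3 consecutive measurements within a 15-minute interval remain above protocol-defined limits despite intervention".
- Table 1 in Section 6.3 ends with "D/C infusion and monitor subject for safety as described in Section 7.4 and 7.5 Event qualifies as DLT". Its earlier steps are holds and reductions such as "dose by 50% (e.g., 0.05mg/kg/hr reduced to 0.025 mg/kg/hr) and continue infusion".
- Section 6.2 fixes the full course: "The infusion will be completely stopped 12 hours after the start of infusion".

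On timing, Section 3.2 states that "our data suggest that ketamine side effects occur with the loading dose", and that dose runs over the first hour.

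Sections 4 and 7 and Appendix 2 also call for an extra blood draw at any adverse event or side effect, to relate symptoms to the plasma level. Section 12 has no pharmacokinetic analysis. No section says how Cmax, AUC or Css is derived after a stop, hold or rate cut.

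**The concern.** An exposure-toxicity analysis needs exposure that precedes the toxicity. Here the DLT during infusion either is the stopping of the drug or leads to it. For that patient the later scheduled samples are washout samples, the AUC is cut short, and no maintenance steady state exists to give a Css. Holds and rate cuts do the same to a lesser degree, including in patients who never reach a DLT.

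The effect runs in one direction. Even if higher concentrations truly cause DLTs, patients with a DLT have their AUC and Css pulled down because they had it. The result could be read as no relation, or an inverse one, between plasma ketamine and toxicity. Section 2.2 notes that no PK/PD models exist for ketamine side effects and calls understanding the concentration-time profile critical. A misleading sign would fall on that gap.

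**Working it through.** The plan gives no figure for this correlation, so there is nothing to reproduce. The checks below size the bias.

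**Inputs from the protocol.** Loading infusion 1 hour; lowest load 0.05 mg/kg/h; ceiling 0.20 mg/kg/h (Section 4; the levels in Figure 2 are not visible, so 0.20 stands for the upper end only); maintenance 0.05 mg/kg/h to hour 12; samples at 1, 6, 10 and 12 hours; at most 12 patients.

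**Assumptions, not in the documents.** One-compartment linear kinetics; half-life 2 to 4 hours (1 hour also tried where stated).

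**1. Delivered dose (needs no half-life).** Completer: load × 1 + 0.05 × 11. Stopped at 1 hour: load × 1.

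- Load 0.05: 0.05 / (0.05 + 0.55) = 0.05 / 0.60 = 8%.
- Load 0.20: 0.20 / (0.20 + 0.55) = 0.20 / 0.75 = 27%.

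**2. Parameters from the four samples.** AUC is the linear trapezoid over 0, 1, 6, 10 and 12 hours, with C(0) = 0:

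AUC = 0.5·C1 + 2.5·(C1 + C6) + 2·(C6 + C10) + 1·(C10 + C12)

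Example with half-life 2 hours and unit volume:

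| Patient | C1 | C6 | C10 | C12 | AUC |
|---|---|---|---|---|---|
| 0.20 load, stopped at 1 h | 0.169 | 0.030 | 0.007 | 0.004 | 0.668 |
| 0.20 load, completed | 0.169 | 0.149 | 0.145 | 0.145 | 1.757 |
| 0.05 load, completed | 0.042 | 0.126 | 0.140 | 0.142 | 1.256 |

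The stopped patient has 0.668 / 1.757 = 38% of the same-load completer's AUC, and 0.668 / 1.256 = 53% of the AUC of a completer on the lowest load.

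Over half-lives of 2 to 4 hours, for the 0.20 load:

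| Stop at | AUC vs same-load completer | AUC vs lowest-load completer |
|---|---|---|
| 1 h | 38% | 53–54% |
| 4 h | 52–58% | 73–81% |
| 8 h | 82–85% | 114–120% |

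- **Css** (mean of the 10 and 12 hour samples) after a 1-hour stop on the 0.20 load is 4–12% of the same-load completer's.
- **Cmax** (highest of the four samples) on the 0.20 load is 32–46% of the same-load completer's after a stop at 0.5 hours, but 67–100% after a stop at 1 hour. At the 0.05 load, where load equals maintenance, it is 18–30% after a 1-hour stop (50% with a 1-hour half-life).

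**3. Sign of the correlation.** Trials of 12 patients were simulated (1,500 per scenario), with three patients at each of the loads 0.05, 0.10, 0.15 and 0.20. Further assumptions were half-life 1 to 4 hours, 30% between-patient variability, DLT hazard proportional to concentration or its square, and infusion stopped at the DLT. Css here is the mean of the 6, 10 and 12 hour samples. The true relation is positive throughout. Each cell gives the mean rank correlation with DLT, with the share of trials showing a negative sign in brackets.

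| Parameter | DLTs spread over 12 h | DLTs in first 2 h |
|---|---|---|
| AUC | −0.06 to −0.28 (57–83%) | −0.53 to −0.68 (98–100%) |
| Css | −0.30 to −0.47 (87–94%) | −0.66 to −0.77 (about 100%) |
| Cmax | +0.20 to −0.21 (25–77%) | +0.18 to −0.55 (27–98%) |

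Replacing the observed AUC with the AUC predicted for the full planned infusion brings the mean correlation back to +0.15 to +0.43. The sign is still wrong in 5–31% of trials, which reflects the small sample.

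**The case against.** The strongest reply is that the plan already has the right tool. Any side effect or adverse event triggers a blood draw, so concentrations at the event will be available. A reader might infer from this point that the trial cannot link side effects to plasma levels, and the documents do not support that. What remains is narrower: the samples named for the DLT correlation are the scheduled ones, and event-free patients have no triggered sample at a matching time.

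Other limits also stand.

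- It is tempting to say that every DLT lowers exposure. A DLT first occurring after hour 12 cannot, and Section 3.4.1 watches for events until hour 24.
- It is tempting to say that DLT patients will have the lowest AUC in the trial. That depends on an early stop. At 8 hours on the 0.20 load the AUC still exceeds that of a lowest-load completer.
- Cmax often survives a stop that comes after the 1-hour sample on a high load.
- The protocol states no AUC interval. Taking it as 0 to 12 hours is a reading, although the named samples span that period and no truncation rule is given.
- PK is not among the objectives or endpoints in Section 3, and with at most 12 patients any correlation is descriptive.

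The last point lowers the weight of the issue but does not remove it. Small numbers add noise, whereas this is a bias of known direction.

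**Conclusion.** The concern holds for AUC and Css. Followed as written, the plan correlates DLTs with exposure that the DLT has reduced, and the correlation is biased toward zero or the wrong sign. The bias is largest for early DLTs, which the protocol itself expects. It shrinks for late stops and vanishes for DLTs first occurring after hour 12. Cmax is affected mainly when the stop falls inside the loading hour or at the lowest load.

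The delivered-dose percentages rest only on the protocol's rates and the 1-hour stop chosen for illustration. The AUC, Css and Cmax percentages and the simulated correlations depend on the assumed kinetics, dose levels and hazard. The negative average for AUC and Css held in every scenario tried.

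A reader might infer that the MTD is compromised. It is not: escalation and the MTD rest on DLT counts and do not use this analysis. The point is worth correcting before the data are analyzed, as a secondary matter.

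**What to change.** Replace the sentence in Section 7 with:

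> Cmax, AUC and Css will be reported descriptively, with Css only for patients whose maintenance rate was unchanged. DLTs will not be correlated with AUC or Css that include time after a stop, hold or rate cut made for the event. DLTs will be related to exposure up to the event: the event-triggered concentration, and cumulative dose or AUC to the event time. Each will be compared with the value at the same elapsed time in patients still event-free and on infusion, interpolated or model-predicted from actual infusion rates, which will be recorded.

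A simpler alternative is to relate DLTs to the assigned loading dose and to the exposure predicted for the planned infusion.

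The comparators must be cut at the same elapsed time. Truncating only the DLT patient would make matters worse: on the 0.20 load, AUC to a 1-hour event is roughly 3–5% of a same-load completer's 12-hour AUC.

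**Cost.** Dosing and the sampling schedule do not change. Because event-free patients are sampled only at 1, 6, 10 and 12 hours, time-matching needs interpolation or some PK modelling. Rate changes must be recorded with their times; Sections 6.2 and 7.3 allow adjustments but do not describe such a record. Fewer patients will contribute a Css.
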